5.3.2. Additional considerations

Considering that RCC are available and the percentage of subjects with titres/concentration above key thresholds are available, the distribution of antibody concentrations or titres of each antigen will not be tabulated.

Following the re-validation of the pertussis assays, the booster response to the PT, FHA and PRN antigens is defined as:

- for subjects with pre-vaccination antibody concentration below the assay cut-off, post-vaccination antibody concentration \geq four times the assay cut-off,
- for subjects with pre-vaccination antibody concentration between the assay cut-off and below four times the assay cut-off, post-vaccination antibody concentration \geq four times the pre-vaccination antibody concentration, and
- for subjects with pre-vaccination antibody concentration \geq four times the assay cut-off, post-vaccination antibody concentration \geq two times the pre-vaccination antibody concentration

Percentage of subjects with anti-pneumococcal serotypes (1, 3, 4, 5, 6A, 6B, 7F, 9V, 14, 18C, 19A, 19F, 23F) above the assay cut-offs, will be calculated along with its exact 95% CI [[Clopper](#), 1934].

In addition to the percentage of seroprotected or seropositive subjects, the percentage of subjects above the assay cut off and percentage of subjects above the following cut-off will be summarized

- Anti-PRP antibody concentrations \geq 1.0 $\mu\text{g/mL}$.
- Anti-diphtheria antibody concentrations \geq 1.0 IU/mL.
- Anti-tetanus antibody concentrations \geq 1.0 IU/mL.
- Anti-HBs antibody concentrations \geq 100 mIU/mL.
- Anti-pneumococcal serotypes (1, 3, 4, 5, 6A, 6B, 7F, 9V, 14, 18C, 19A, 19F, 23F) \geq 0.35 $\mu\text{g/mL}$.

In addition, subgroups analysis according to gestational age (27-32 weeks and 33-36 weeks) and age of the mother at dose 1 in the primary study (18-24 year, 25-34 year and 35-45 year) will be performed.

The sub-group analyses will be limited to descriptive tables of GMT/GMC and the percentage of subjects with titres/concentration above key thresholds for ATP cohort of immunogenicity.

In light of the number of subjects enrolled in each country, the analysis by country will be replaced with analysis by schedule of the primary vaccination (2 doses ie 2,4 months combined with 3,5 months versus 3 doses i.e. 2,3,4 months combined with 2,4,6 months).

The immunogenicity analysis for the pertussis antigens will be generated on the adapted ATP cohort taking in to account all the time points from the study Boostrix 047 up to the current study.

The kinetics of the observed GMCs of the pertussis antigens across all the time points will be plotted in an evolution graph with confidence interval.

5.4. Analysis of safety and reactogenicity

5.4.1. Analysis of safety and reactogenicity planned in the protocol

The primary analysis will be based on the TVC. If more than 5% of enrolled subjects are excluded from the ATP cohort for analysis of safety, then a second analysis based on this ATP cohort will be performed to complement the TVC analysis. All analyses will be descriptive.

- The percentage of subjects with at least one local symptom (solicited or unsolicited), with at least one general symptom (solicited or unsolicited) and with any symptom (solicited or unsolicited) during the 4-day (Day 0-Day 3) solicited follow-up period will be tabulated with exact 95% CI [Clopper, 1934]. The same calculations will be done for symptoms (solicited or unsolicited) rated as grade 3 in intensity, for symptoms (solicited or unsolicited) leading to medical advice and for symptoms (solicited or unsolicited) assessed as causally related to vaccination.
- The incidence of local AEs (solicited and unsolicited) will be calculated at each injection site as well as overall (all sites considered) for each group.
- The percentage of subjects reporting each individual solicited local and general symptom during the 4-day (Day 0-Day 3) solicited follow-up period will be tabulated after the vaccine dose, with exact 95% CI [Clopper, 1934]. The same calculations will be done for each individual solicited symptom rated as grade 3 in intensity and for each individual solicited symptom assessed as causally related to vaccination.
- All computations mentioned above will be done for Grade ≥ 2 (solicited symptoms only) and grade 3 symptoms, for symptoms considered related to vaccination (general symptoms only), for grade 3 symptoms considered related to vaccination (general symptoms only) and for symptoms that resulted in a medically-attended visit.
- Occurrence of fever and related fever will be reported per 0.5°C cumulative temperature increments as well as the occurrence of grade 3 fever ($> 39.0^{\circ}\text{C}$ axillary temperature) with causal relationship to vaccination.

- The verbatim reports of unsolicited AEs will be reviewed by a physician and the signs and symptoms will be coded according to MedDRA. Every verbatim term will be matched with the appropriate Preferred Term. The percentage of subjects with unsolicited AEs occurring within 31-day (Day 0- Day 30) follow-up period after any dose with its exact 95% CI [Clopper, 1934] will be tabulated by group, and by preferred term. Similar tabulation will be done for unsolicited AEs rated as grade 3, for unsolicited AEs with causal relationship to vaccination and AEs/SAEs leading to withdrawal from the study.
- The percentage of subjects who receive concomitant medication and antipyretic medication during the 4-day (Day 0- Day 3) follow-up period and during the entire study period will be tabulated (with exact 95% CI [Clopper, 1934]) after the booster dose.
- Any large injection site reaction (defined as any local swelling with diameter > 50 mm and/or any noticeable diffuse injection site swelling (diameter not measurable) and/or any noticeable increased circumference of the injected limb) reported within 4 days (Day 0-Day 3) following the booster dose will be described in detail.
- Subjects who experience at least one SAE from booster vaccination up to study end will be described in detail.
- Subjects who report at least one SAE after the end of primary study 201330 [DTPA (BOOSTRIX)-048 PRI] and before 201334 [DTPA (BOOSTRIX)-049 BST: 048] study will be described in detail.
- Withdrawal due to AEs and SAEs following vaccinations will be described in detail.
- For the subjects who withdraw from the study after Visit 1 (after completion of ASQ-3 questionnaire but have not received booster vaccination), the analysis will be performed on the Total enrolled cohort.
- Neurodevelopmental status of the subjects will be assessed depending on the ASQ-3 score. The proportion of subjects in the black zone for any domain, for gross motor skills, fine motor skills, communication, problem solving skills and personal-social skills will be tabulated. The proportion of infants referred for formal neurodevelopmental evaluation using BSID-III and those with at least one indicators of neurodevelopmental impairment using BSID-III will also be tabulated.

Handling of missing data:

- For a given subject and the analysis of solicited AEs, four days post-vaccination (Day 0-Day 3), missing or non-evaluable measurements will not be replaced. Therefore, the analysis of the solicited AEs based on the TVC will include only vaccinated subjects and doses with documented safety data (i.e., symptom screen completed).
- For a given subject, missing neurodevelopmental status will not be replaced. Therefore, an analysis will exclude subjects with missing or non-evaluable measurements

- For analysis of unsolicited AEs, such as SAEs or AEs by primary Medical Dictionary for Regulatory Activities (MedDRA) term, and for the analysis of concomitant medications, all vaccinated subjects will be considered. Subjects, whose parent(s)/LAR(s) do not report the event or the concomitant medication, will be considered as subjects without the event or the concomitant medication, respectively.
- For summaries reporting both solicited and unsolicited AEs, all vaccinated subjects will be considered. Subjects, whose parent(s)/LAR(s) do not report the event or the concomitant medication, will be considered as subjects without the event or the concomitant medication, respectively.

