**Table 4 List of study procedures**

**(Amended 12 December 2016)**

Age	9 months	11-18 months	12-19 months	18 months **
Epoch	Epoch 001			
Type of contact	Visit 1	Visit 2	Visit 3	Phone contact *
Time points	Months -2 to -9	Day 0 **	Month 1 **	Day 0 to Month7 **
Sampling time points		Pre-Bst	Post-Bst	
Informed consent	●			
Check inclusion/exclusion criteria	●			
Collect demographic data		●		
Medical history, including medication/vaccine history §	●	●		
Physical examination		○		
Check contraindications and warnings and precautions		○		
Pre-vaccination body temperature		●		
Measure/record length, weight and head circumference		●		
Vaccine				
Treatment number allocation		○		
Recording of administered treatment number		●		
Vaccine administration		●		
Laboratory assays				
Blood sampling for antibody determination (approx 5 mL)		●	●	
Safety assessments				
Record any concomitant medication/vaccination		●	●	
Record any intercurrent medical conditions			●	
Distribution of diary cards		●		
Recording of solicited adverse events (Day 0-Day 3) post-vaccination by subjects' parent(s)/LAR(s) in the diary card		●		
Recording of non-serious adverse events within 31 days (Day 0-Day 30) post-vaccination, by subjects' parent(s)/LAR(s) in the diary card		●	●	
Recording of large injection-site reactions		●		
Return of diary cards			○	
Diary card transcription by investigator or site staff			●	
Recording of neurodevelopmental status by the subjects' parent(s)/LAR(s) in the ASQ-3 paper questionnaire	●	● **	● **	● **
Transcribe the information in ASQ-3 paper questionnaire, by the investigator	●	● **	● **	● **
Recording of SAEs and AEs/SAEs leading to withdrawal	●	●	●	● **
Recording of SAEs related to study participation or to a concurrent GSK medication/vaccine	●	●	●	●
Study Conclusion †				●

● is used to indicate a study procedure that requires documentation in the individual eCRF.

○ is used to indicate a study procedure that does not require documentation in the individual eCRF.

\* **For Czech Republic, the phone call at 18 months may be replaced by a clinic visit if deemed preferable by the study team.**

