### **6.7.1. Recording of concomitant medications/products and concomitant vaccinations**

The following concomitant medication(s)/product(s)/vaccine(s) must be recorded in the eCRF.

- All concomitant medications/products, except vitamins and dietary supplements, administered during the period starting from the administration of the dose of study vaccines (Visit 2) and ending at Visit 3 (**Day 0 to Day 30**)
- Any concomitant vaccination administered in the period starting from the administration of the dose of study vaccines (Visit 2) and ending at the study visit 3 (**Day 0 to Day 30**).

Note: Medications/vaccinations listed prior to the dose of study vaccine are to be recorded as medical/vaccination history.

- Prophylactic medication (i.e., medication administered in the absence of ANY symptom and in anticipation of a reaction to the vaccination).

E.g., an anti-pyretic is considered to be prophylactic when it is given in the absence of fever and any other symptom, to prevent fever from occurring [fever is defined as temperature  $\geq 37.5^{\circ}\text{C}/99.5^{\circ}\text{F}$  for oral, axillary or tympanic route, or  $\geq 38.0^{\circ}\text{C}/100.4^{\circ}\text{F}$  for rectal route].

- Any concomitant medications/products/vaccines listed in Section 6.7.2.
- Any concomitant medications/products/vaccines relevant to a SAE to be reported as per protocol or administered at any time during the study period for the treatment of a SAE. In addition, concomitant medications relevant to SAEs need to be recorded on the expedited Adverse Event report.

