- The verbatim reports of unsolicited AEs will be reviewed by a physician and the signs and symptoms will be coded according to MedDRA. Every verbatim term will be matched with the appropriate Preferred Term. The percentage of subjects with unsolicited AEs occurring within 31-day (Day 0- Day 30) follow-up period after any dose with its exact 95% CI [Clopper, 1934] will be tabulated by group, and by preferred term. Similar tabulation will be done for unsolicited AEs rated as grade 3, for unsolicited AEs with causal relationship to vaccination and AEs/SAEs leading to withdrawal from the study.
- The percentage of subjects who receive concomitant medication and antipyretic medication during the 4-day (Day 0- Day 3) follow-up period and during the entire

study period will be tabulated (with exact 95% CI [Clopper, 1934]) after the booster dose.

- Any large injection site reaction (defined as any local swelling with diameter > 50 mm and/or any noticeable diffuse injection site swelling (diameter not measurable) and/or any noticeable increased circumference of the injected limb) reported within 4 days (Day 0-Day 3) following the booster dose will be described in detail.
- Subjects who experience at least one SAE from booster vaccination up to study end will be described in detail.
- Subjects who report at least one SAE after the end of primary study 201330 [DTPA (BOOSTRIX)-048 PRI] and before 201334 [DTPA (BOOSTRIX)-049 BST: 048] study will be described in detail.
- Withdrawal due to AEs and SAEs following vaccinations will be described in detail.
- For the subjects who withdraw from the study after Visit 1 (after completion of ASQ-3 questionnaire but have not received booster vaccination), the analysis will be performed on the Total enrolled cohort.
- Neurodevelopmental status of the subjects will be assessed depending on the ASQ-3 score. The proportion of subjects in the black zone for any domain, for gross motor skills, fine motor skills, communication, problem solving skills and personal-social skills will be tabulated. The proportion of infants referred for formal neurodevelopmental evaluation using BSID-III and those with at least one indicators of neurodevelopmental impairment using BSID-III will also be tabulated.

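### Medication use is to be reported for the whole study after the booster, but general recording stops at Visit 3 and unreported use counts as none, so the percentage can only be too low

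*SAP*

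**What the plan says.** **Analysis.** Protocol 10.8, repeated in SAP 5.4.1, plans "The percentage of subjects who receive concomitant medication and antipyretic medication during the 4-day" period after vaccination and a second period covering the whole study. The SAP wording is "follow-up period and during the entire study period will be tabulated (with exact 95% CI [Clopper, 1934]) after the booster dose".

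**Collection.** Protocol 6.7.1 asks for all concomitant medication, apart from vitamins and dietary supplements, "administered during the period starting from the administration of the dose of study vaccines (Visit 2) and ending at Visit 3", with Day 0 to Day 30 given in brackets. In Table 4 the row "Record any concomitant medication/vaccination" is marked at Visits 2 and 3 and is empty at the 18-month contact. Section 6.7.1 has wider categories too: "Any concomitant medications/products/vaccines listed in Section 6.7.2", and medication relevant to a reportable serious adverse event or "administered at any time during the study period for the treatment of a SAE". Earlier use is kept apart: "Medications/vaccinations listed prior to the dose of study vaccine are to be recorded as medical/vaccination history".

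**Missing reports.** For concomitant medication, SAP 5.4.1 uses all vaccinated infants as the denominator. Those whose parents "do not report the event or the concomitant medication, will be considered as subjects without the event or the concomitant medication, respectively".

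**Length of follow-up.** Protocol Section 3 and SAP Section 2 run each infant from 9 months of age to the 18-month contact, or to Visit 3 if that is later. The booster is given between 11 and 18 months.

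**The concern.** The reporting period extends beyond the collection period. An infant who first takes an antipyretic between Visit 3 and the 18-month contact would normally leave no trace in the database, and the missing-report rule then turns that silence into a definite non-use. The resulting percentage would be presented as post-booster use over the whole study, with an exact confidence interval that carries only sampling error and no allowance for the uncollected time.

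The rest of the safety plan does not have this problem. Unsolicited events are collected and tabulated over Day 0-30. Serious events are collected until discharge and described to study end. Medication is the item for which the two periods differ.

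**Working it through.** **Inputs**
- Start of study: 9 months of age (Protocol Section 3).
- Booster age *b*: 11 to 18 months (Protocol Section 3, SAP Section 2).
- Visit 3: nominally one month after the booster, allowed at 21-48 days (Protocol Table 5).
- End of follow-up: 18-month contact, or Visit 3 if later. The contact is allowed from 17 months 0 days to 18 months 30 days (Protocol Table 5).

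**The plan's own figures.** 18 − 9 = 9 and 19 − 9 = 10 months, which reproduces the stated duration of about 9 to 10 months. From booster to contact, 18 − 18 = 0 and 18 − 11 = 7 months, which reproduces the Day 0 to Month 7 range in Table 4.

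**Recording gap after the booster.** End = max(18, *b* + 1). Post-booster time = End − *b*. Unrecorded time = End − (*b* + 1).

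| Booster age (months) | Visit 3 | End | Post-booster months | Unrecorded months | Share recorded |
|---|---|---|---|---|---|
| 11 | 12 | 18 | 7 | 6 | 14% |
| 12 | 13 | 18 | 6 | 5 | 17% |
| 13 | 14 | 18 | 5 | 4 | 20% |
| 15 | 16 | 18 | 3 | 2 | 33% |
| 16 | 17 | 18 | 2 | 1 | 50% |
| 17 | 18 | 18 | 1 | 0 | 100% |
| 18 | 19 | 19 | 1 | 0 | 100% |

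Taking the allowed windows to their limits for a booster at 11 months, with 30.4 days to the month:
- Shortest gap: 17 − (11 + 48/30.4) = 4.4 months.
- Longest gap: (18 + 30/30.4) − (11 + 21/30.4) = 7.3 months.

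**Direction.** An infant who uses medication inside the recorded window is counted whatever happens later. An infant who uses it only afterwards is counted as a non-user. The reported percentage can therefore equal or fall below the true one, but cannot exceed it.

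**Size, as illustration only.** The documents give no usage rate. Assume a constant, independent monthly probability *q* of any use. The table reports *q*; the true whole-period figure is 1 − (1 − *q*)^(post-booster months).

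| *q* = reported | True, booster at 11 mo | True, 15 mo | True, 17-18 mo | Understatement (points) |
|---|---|---|---|---|
| 10% | 52.2% | 27.1% | 10.0% | 42.2 / 17.1 / 0 |
| 30% | 91.8% | 65.7% | 30.0% | 61.8 / 35.7 / 0 |
| 50% | 99.2% | 87.5% | 50.0% | 49.2 / 37.5 / 0 |

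**Does the SAP repair it elsewhere?** SAP 5.4.2 and Section 8 do not redefine the period. Template 23, the medication mock table, covers Days 0-3 only.

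**The case against.** The best defence is that this concerns the label of one descriptive table. No listed primary or secondary endpoint is a medication measure, and all analyses are descriptive. The final title cannot be seen either: the list of tables is held outside the SAP, and the mock titles are to be adapted. All of that is true and keeps the point minor. The analysis text nevertheless specifies the period, and a programmer following it would produce the understated percentage.

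A second defence is that some later medication is captured. Protocol 6.7 has the investigator ask at every visit or contact. Section 6.7.1 keeps Section 6.7.2 products and medication linked to serious events, and its line on prophylactic medication has no date limit. Section 8.5 wants treatment of any adverse event recorded. This defeats the inference that nothing is collected after Visit 3. It does not close the gap: asking is not recording, Table 4 has no medication entry at the contact, and non-serious events are recorded only to Day 30. Routine medication and ordinary antipyretics after Visit 3 remain outside the recording rule.

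A reader might also infer that comparisons of medication use by country or primary schedule would be distorted. The gap does vary with booster age, but no such comparison is planned. The country and schedule breakdowns belong to immunogenicity (Protocol 10.7, SAP 5.3.1 and 5.3.2), and Template 23 has only dTpa and Control columns.

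**Conclusion.** The plan is wrong as written, on a minor descriptive safety output. The percentage for the whole study after the booster is biased downward for any infant whose Visit 3 precedes the 18-month contact. The nominal unrecorded share runs from 6 of 7 months for a booster at 11 months to none at 17 or 18 months.

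The error in percentage points cannot be derived from the documents. Under assumed monthly probabilities of 10% to 50% it lies between 0 and about 62 points, depending on booster age. No single figure from that range should be quoted as the expected error. A constant rate is doubtful for antipyretics in particular, because the recorded month includes the days just after vaccination.

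It would also go too far to read this as bias between the groups. Both follow the same national or local schedules, and nothing in the documents suggests that the gap differs systematically between them. The Day 0-3 table is unaffected.

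This conclusion takes the table to cover post-booster time, as its wording indicates. Read from Visit 1 with pre-dose history left out, the unrecorded time would be about 8 to 9 months at every booster age.

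**What to change.** In Protocol 10.8 and SAP 5.4.1, replace the whole-study period for medication with the period from the booster dose to the actual date of Visit 3, for which Section 6.7.1 requires recording. Title the table to match, and apply the rule that unreported means not taken, for medication, only within that window. The recording gap is then zero at every booster age.

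A fixed Day 0-30 window is an alternative, but the two should not be written as if they were the same. Visit 3 is allowed at 21-48 days, so an infant seen on Day 21 would have 30 − 21 = 9 days of a fixed window after the visit. One definition should be chosen and the bracketed days in Section 6.7.1 aligned with it.

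The cost is a change of wording and a table title, with no new data collection. The downside is that the report no longer offers a figure for medication use over the whole study, which the collection rules could not support.

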Currently, the effect of *Boostrix* administered to mothers during pregnancy or immediately post-delivery on the neurodevelopment of infants is unknown. Therefore, the neurodevelopment of the subjects will be studied at 9 months and 18 months of age in this study. To assess the neurodevelopmental status, the ***investigator or designate*** will complete a standardised developmental screening tool, Ages and Stages Questionnaire-3 (ASQ-3) via a paper questionnaire ***with subjects' parent(s)/LAR(s) during the study visits or phone call*** [ASQ-3, 2016]. (Amended 12 December 2016)

Any subject who scores below the cut-off i.e., a score more than 2 Standard Deviations (SDs) below the mean score for the U.S. reference group (i.e., black zone in the score chart) in any of the five domains of the ASQ-3 (i.e., communication, gross motor, fine motor, problem solving, and personal-social) will be referred to a developmental specialist for formal neurodevelopmental assessment (e.g., using the Bayley Scale for Infant Development, Version III [BSID-III]) [Bayley-III, 2006]. An overall neurodevelopmental assessment in the areas of cognitive, language, motor, social-emotional and adaptive behaviour will be rendered using BSID-III. A BSID-III score more than 2 SDs below the mean score for the U.S. reference group will be considered as a neurodevelopmental impairment.

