3.4. Secondary endpoints

- Immunogenicity with respect to components of *Infanrix hexa* and *Prevenar 13*.

Before the booster dose

- Anti-diphtheria, anti-tetanus, anti-poliovirus type 1, anti-poliovirus type 2, anti-poliovirus type 3, anti-HBs and anti-PRP seroprotection status.
- Anti-PT, anti-FHA and anti-PRN and anti-pneumococcal serotypes (1, 3, 4, 5, 6A, 6B, 7F, 9V, 14, 18C, 19A, 19F, 23F) seropositivity rates.
- Anti-diphtheria, anti-tetanus, anti-PT, anti-FHA, anti-PRN, anti-poliovirus type 1, anti-poliovirus type 2, anti-poliovirus type 3, anti-HBs and anti-pneumococcal serotypes (1, 3, 4, 5, 6A, 6B, 7F, 9V, 14, 18C, 19A, 19F, 23F) and anti-PRP antibody concentrations or titres.

One month after the booster dose

- Anti-diphtheria, anti-tetanus, anti-poliovirus type 1, anti-poliovirus type 2, anti-poliovirus type 3, anti-HBs, anti-PRP, anti-PT, anti-FHA, anti-PRN and anti-pneumococcal serotypes (1, 3, 4, 5, 6A, 6B, 7F, 9V, 14, 18C, 19A, 19F, 23F) antibody concentrations or titres.
- Anti-PT, anti-FHA, anti-PRN antibody seropositivity rates.
- Solicited local and general symptoms.
 - Occurrence of solicited local/general symptoms during the 4-day (Day 0-Day 3) follow-up period after booster vaccination.
- Unsolicited adverse events.
 - Occurrence of unsolicited symptoms during the 31-day (Day 0-Day 30) follow-up period after booster vaccination.
- Serious adverse events.
 - Occurrence of reported SAEs from booster dose up to study end.
- Neurodevelopmental status will be assessed at 9 and 18 months of age adjusted for prematurity.
 - Proportion of infants with an ASQ-3 score in the black zone in any domain.
 - Proportion of infants with an ASQ-3 score in the black zone for gross motor skills.
 - Proportion of infants with an ASQ-3 score in the black zone for fine motor skills.
 - Proportion of infants with an ASQ-3 score in the black zone for communication.
 - Proportion of infants with an ASQ-3 score in the black zone for problem solving skills.
 - Proportion of infants with an ASQ-3 score in the black zone for personal-social skills.
 - Proportion of infants referred for formal neurodevelopmental evaluation using BSID-III.

- Proportion of infants with at least one of the indicators of neurodevelopmental impairment using BSID-III.

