9.1.2. Ages & Stages Questionnaires (ASQ-3)

For the ASQ-3 analysis: The threshold value (cut off corresponding to the black zone) for each of the domain at time point month 9 and 18 are as follows [Squires, J., & Bricker, D., 2009].

Domain	Cut off (Month 9)	Cut off (Month 18)
Communication	13.97	13.06
Gross Motor	17.82	37.38
Fine motor	31.32	34.32
Problem Solving	28.72	25.74
Personal –Social	18.91	27.19

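### Every planned ASQ-3 output is a proportion below a −2 SD cut-off; adding domain-score summaries would describe a shift in development more precisely at little cost

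*SAP*

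**What the plan says.** Protocol 1.2.2 states that the effect of maternal Boostrix "on the neurodevelopment of infants is unknown" and that for this reason "the neurodevelopment of the subjects will be studied at 9 months and 18 months of age in this study". Neurodevelopmental status is a secondary objective (Protocol 2.2, SAP 3.2).

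The black zone is defined as "a score more than 2 Standard Deviations (SDs) below the mean score for the U.S. reference group". The endpoints follow that cut: SAP 3.4 starts with "Proportion of infants with an ASQ-3 score in the black zone in any domain" and then lists each of the five domains. SAP 5.4.1 tabulates "The proportion of subjects in the black zone for any domain, for gross motor skills, fine motor skills, communication, problem solving skills" and the personal-social domain, and adds "The proportion of infants referred for formal neurodevelopmental evaluation using BSID-III" and BSID-III impairment. SAP 5.4.2 adds only that the tabulation is done at both months 9 and 18. Templates 29–31 (SAP Annex 3) show these results as counts and percentages on the Total enrolled cohort. Neither document plans a mean, median or distribution of ASQ-3 scores.

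SAP 9.1.2 gives "The threshold value (cut off corresponding to the black zone) for each of the domain at time point month 9 and 18", for example 13.97 and 13.06 for communication and 17.82 and 37.38 for gross motor. Protocol Table 4 includes the step "Transcribe the information in ASQ-3 paper questionnaire, by the investigator", marked as requiring documentation in the eCRF.

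**The concern.** A cut at −2 SD uses only whether an infant falls in the extreme lower tail. If one group's scores were moderately lower throughout, most of the evidence would lie in the body of the distribution, which the planned tables do not show. With no marked difference in black-zone rates, readers could take more reassurance from these tables than they can give, on a question that the protocol itself calls open.

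The SAP treats other measurements more fully. Antibodies get threshold percentages plus geometric means and reverse cumulative curves (SAP 5.3.1). Fever is reported per 0.5°C increment (SAP 5.4.1). Head circumference gets mean, SD, median and quartiles (Template 8).

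**Working it through.** **The plan's own figures.** The documents state no precision or power for ASQ-3. The only sample-size figures are for immunogenicity (Protocol 10.3): 340 × 0.80 = 272, 340 × 0.70 = 238 and 340 × 0.60 = 204 evaluable per group. These reproduce, and so do all 33 exact intervals in Table 16, within 0.1 point. They are not the ASQ-3 denominator. Templates 29–31 use the Total enrolled cohort, at most about 340 per group (Protocol 5.2.2.1.1).

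**Inputs.** Cut-off c = −2 SD (Protocol 1.2.2); N = 340 per group; scores assumed normal with the reference mean and SD. The documents give no ASQ-3 distribution.

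**Information kept by the cut.** For a small uniform shift in one domain, the efficiency of the proportion relative to the mean is φ(c)² / [Φ(c)(1 − Φ(c))].
- φ(2) = 0.0540; Φ(−2) = 0.02275.
- 0.0540² / (0.02275 × 0.97725) = 0.131, a loss of 86.9%.
- 0.131 × 340 ≈ 45: the dichotomised data of 340 infants carry the information of about 45 analysed as a mean.

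**Half-width of a group difference, 340 per group.**
- Single-domain rate: 1.96 × √(2 × 0.02275 × 0.97725 / 340) = 2.24 points.
- As a shift, to first order: 0.0224 / 0.0540 = 0.415 SD.
- Mean score: 1.96 × √(2 / 340) = 0.150 SD.

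If missing forms reduced N to 272, for illustration, these become 2.5 points, 0.46 SD and 0.17 SD. The efficiency ratio does not depend on N.

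**A finite shift.** A uniform 0.2 SD worsening moves a domain's rate from 2.28% to 3.59%. At a two-sided 0.05 level (assumed; the plan sets none), 80% power would need 393 per group for means and 2573 for proportions. The ratio is 2573 / 393 = 6.5, close to the small-shift value 1 / 0.131 = 7.6.

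**Sensitivity of the loss to the assumptions.**

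| Assumption | Information lost |
|---|---|
| Normal, one domain | 87% |
| Logistic or t with 5 df | 92–94% |
| Left-skewed gamma | 90–93% |
| Normal with a ceiling 0.5–1.5 SD above the mean | 75–85% |
| Normal, 5% or 10% of infants below the cut | 78% or 66% |
| Any-domain row against a five-domain composite mean, correlation 0 | 88% |
| The same, correlations 0.2–0.8 | 75–81% |

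**Infants behind each percentage.** One domain: 340 × 0.02275 ≈ 8 per group. Any domain, if the five were independent: 1 − 0.97725⁵ = 10.9%, and 340 × 0.109 ≈ 37; fewer if domains are correlated.

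**The case against.** The cut-off is not an arbitrary dichotomy. Protocol 5.6.2.13 presents ASQ-3 as a screening tool that identifies children needing in-depth assessment, and a black-zone score triggers referral. The endpoints are protocol-defined proportions, the objective is to assess status, and neither document says how to interpret a mean score. If harm were confined to a small low-scoring subgroup, the tail proportion would be the right measure. All of this stands, and it is why the existing endpoints should stay.

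The study is also descriptive, with no planned test or group contrast (SAP 6). What is lost is therefore precision in comparing the groups, not a stated power, and no planned result becomes wrong.

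Several stronger readings are tempting, but the documents do not support them:
- **That 87% of the information is lost, as a fact.** This needs normal scores, a single domain and a small uniform shift. It does not carry over to the any-domain row.
- **That a modest shift would be invisible.** The rates do move, as the 2.28% to 3.59% example shows, but imprecisely.
- **That maternal exposure would act as a uniform shift.** The documents say only that the effect is unknown.
- **That the five scores are stated to be stored.** Table 4 refers to transcribing the questionnaire's information, and its footnote names only referral and the specialist's overall assessment for the eCRF. The numeric cut-offs in SAP 9.1.2 make the inference strong, but it remains an inference.
- **That every percentage rests on a handful of infants.** This is true per domain, not for the any-domain row.

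**Conclusion.** The point holds as an improvement in precision for a secondary objective. All planned ASQ-3 outputs are threshold proportions, although numeric scores are almost certainly available. For a uniform shift, every assumption tried loses at least about two-thirds of the information. At 340 per group, a single-domain black-zone comparison resolves about 0.42 SD, against about 0.15 SD for the mean score; both widen if fewer infants have forms at 18 months. The SD equivalents rest on normality and a first-order conversion. The primary immunogenicity analysis is unaffected.

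**What to change.** Keep the black-zone and BSID-III endpoints unchanged. Add to SAP 5.4.2, for each of the five domains at 9 and 18 months, on the Total enrolled cohort with available scores:

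- N, mean, SD, median and quartiles by group;
- a reverse cumulative curve by group;
- the between-group difference in mean score with a 95% CI, labelled descriptive.

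Confirm first that the domain scores are held in the eCRF. The section already adds an analysis beyond the protocol (congenital anomalies), so there is a precedent. No visit, sample or endpoint changes.

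The cost is one table and figure set, that is, ten more descriptive summaries (5 domains × 2 ages) to read. ASQ-3 scores are bounded and probably skewed, so the gain may be smaller than normal theory suggests. The medians, quartiles and curves guard against relying on the mean alone.
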